### 2.4 DEFINITIONS

- **Mapping success:** It will be defined as complete PVC abolition after RF applications at the earliest activation site (EAS) identified using the assigned mapping approach. A maximum of 2 RF applications with appropriate parameters (contact force, impedance drop, catheter stability) during a maximum of 45 seconds will be allowed. If the PVC is not abolished after 2 RF applications with appropriate parameters, mapping will not be considered successful.
- **Acute procedure success:** It will be defined as complete elimination of the PVC at the end of the procedure.

- **Target point:** It will be defined as any suspected PVC-SOO where RF is delivered according to mapping data. Therefore, for one case there can be found a single target point with multiple RF applications, or multiple target points with one single RF application. The maximum distance between 2 RF applications to be considered at the same target point will be defined as 5 mm (equivalent to a 1-cm^2 area).
- **First mapped chamber:** It will be defined as the first cardiac chamber where the operator decides to perform electroanatomical mapping according to electrocardiographic (PVC morphology) and clinical criteria. In the case of PVCs arising from ventricular outflow tracts, we propose an algorithm (see Appendix C) to avoid subjective criteria, and to deal with eventual wrong selection of the first mapped chamber, leading to unnecessary RF applications.

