#### 4.5.4 ABLATION

Ablation will be directed to the earliest activation site identified with the assigned annotation system. A target point will be defined as any suspected PVC-SOO, where RF is delivered, according to mapping data. The temperature limit will be set at 45°C. Power limit will be set according to the anatomical structure containing the SOO: 40 W for the RVOT and the subvalvular LVOT, 30-40 W in the aortic root, and 20 W in the coronary sinus. If RF application is successful, it will be maintained for 60 seconds in cases of RVOT PVCs, and for 30-45 seconds when PVCs arise from the LVOT or distal CS. The point at which radiofrequency application is successful will be tagged as the effective RFp (e-RFp). If PVCs persist after a 30-second application, RF delivery will be stopped and another target point will be selected for further applications. Any additional RF applications located within a 6-mm distance from the first application will be considered as part of the same target point–suspected SOO. On the contrary, all RF applications located beyond this 6-mm distance will be considered as additional target points.

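### Section 4.5.4 sends the operator to another target point after one failed 30-second application, while the primary endpoint in section 2.4 allows two at the earliest activation site; the same-target distance also differs (5 mm against 6 mm).

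*Combined protocol and SAP*

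**What the plan says.** Section 2.5.1 makes mapping success the primary endpoint and refers to section 2.4 for its meaning. Section 5.1 bases the sample size on the same definition.

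- **Attempts, section 2.4.** At the EAS, "A maximum of 2 RF applications with appropriate parameters (contact force, impedance drop, catheter stability) during a maximum of 45 seconds will be allowed". Failure is defined to match: "If the PVC is not abolished after 2 RF applications with appropriate parameters, mapping will not be considered successful". The footnote in Appendix B also allows up to two applications at the EAS, each under 45 seconds.
- **Attempts, section 4.5.4.** "If PVCs persist after a 30-second application, RF delivery will be stopped and another target point will be selected for further applications".
- **Repeat applications.** The target-point definition in section 2.4 accepts that "there can be found a single target point with multiple RF applications".
- **Same-target distance, section 2.4.** "The maximum distance between 2 RF applications to be considered at the same target point will be defined as 5 mm".
- **Same-target distance, section 4.5.4.** "Any additional RF applications located within a 6-mm distance from the first application will be considered as part of the same target" point, and "all RF applications located beyond this 6-mm distance will be considered as additional target points".
- **Duration of a successful application, section 4.5.4.** "If RF application is successful, it will be maintained for 60 seconds in cases of RVOT PVCs", and for 30 to 45 seconds when the origin is the LVOT or distal coronary sinus.

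The number of target points is the fourth secondary endpoint in section 2.5.2. Section 2.7 plans recruitment at five centres.

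**The concern.** The definition and the operating rule disagree on how many attempts the EAS receives. Section 2.4 defines a target point as a suspected site of origin, so choosing another one means leaving the EAS. An operator who follows section 4.5.4 to the letter delivers one 30-second application there and moves on. An operator who works from section 2.4 delivers two.

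This affects treatment as well as scoring. If the second EAS application would have abolished the PVC, the patient is a mapping success under one practice and cannot be one under the other. The analysis cannot recover the result of an application that was never given.

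There is also a scoring gap. A patient with one failed EAS application whose PVC is then abolished elsewhere does not meet the success definition, and does not meet the stated failure condition of two adequate applications either.

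The distance conflict is simpler: one term has two numerical definitions, and a secondary endpoint counts that term.

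**Working it through.** **1. Sample size, to rule out an error there.** Inputs from section 5.1: success 60% (manual) and 85% (Wavefront), type I error 5%, power 80%. The test is taken as two-sided because the alternative is that the methods are not equal. Allocation is 1:1 (section 2.2).

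Pooled two-proportion formula, with mean rate (0.60 + 0.85)/2 = 0.725:

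n per group = [1.960 × √(2 × 0.725 × 0.275) + 0.842 × √(0.60 × 0.40 + 0.85 × 0.15)]² / 0.25²

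= [1.238 + 0.510]² / 0.0625 = 48.9, so 49 per group and 98 in total. The plan's figure is reproduced.

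**2. Number of EAS attempts, rule against rule.**

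| Situation | Section 2.4 and Appendix B | Section 4.5.4, literal |
|---|---|---|
| First EAS application abolishes the PVC | Success | Success |
| First fails, second at the EAS would abolish it | Success | Second not given; cannot be a success |
| First fails, second at the EAS would also fail | Failure | Second not given; failure condition of two applications not met |

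The rules agree only in the first row. The 30-second stop itself does not conflict with section 2.4, since 30 seconds lies within a 45-second maximum. The conflict is in where the next application goes.

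**3. Same-target distance.** Take a second application at distance d from the first:

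- d up to 5 mm: same target point in both sections.
- d above 5 mm and up to 6 mm: an additional target point under section 2.4, the same one under section 4.5.4.
- d above 6 mm: an additional target point in both.

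As circles, the areas are π × 0.5² = 0.79 cm² and π × 0.6² = 1.13 cm², a ratio of 1.44. This ratio does not say how many applications fall between the limits. The 1-cm² remark in section 2.4 does not settle the choice: a circle of that area has radius √(1/π) = 0.564 cm, or 5.64 mm, while a 1-cm square has a half-side of 5 mm.

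**4. Can an effect on power be derived?** It would need the share of successes that depend on a second EAS application and the share of patients denied one, by arm. The documents give neither. The assumed losses below show how far the answer depends on them (exact power of the uncorrected chi-square test, two-sided 5%, 49 per group):

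| Assumed share of successes lost, manual / Wavefront | Resulting rates | Power |
|---|---|---|
| 0% / 0% | 60.0% vs 85.0% | 81% |
| 2% / 2% | 58.8% vs 83.3% | 78% |
| 5% / 5% | 57.0% vs 80.75% | 73% |
| 5% / 2% | 57.0% vs 83.3% | 83% |
| 2% / 5% | 58.8% vs 80.75% | 67% |

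Even the direction of the change depends on how the losses divide between the arms.

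**The case against.** The best defence is that section 4.5.4 should be read as a whole and alongside section 2.4. The sentence after the instruction to move provides for further applications near the first, counted as the same target. The definition in section 2.4 accepts several applications at one target. Sections 2.5.1 and 5.1 tie the endpoint to section 2.4, and Appendix B repeats the limit of two. On that reading the endpoint has one consistent count, and nothing in section 4.5.4 says that a single failed application is scored as a mapping failure.

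Part of this stands. A second EAS application is not forbidden, and different handling across centres is a possibility that the documents do not show to be a fact. But the sentences relied on only classify applications once given. The one sentence that tells the operator what to do after a failed 30-second application says to choose another target. The distance mismatch is not answered at all, although it reaches the primary endpoint only if being at the EAS is judged by that distance, which section 2.4 does not say.

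Three stronger readings are tempting and are not supported:

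- **The 60-second RVOT hold breaks the 45-second cap.** Appendix B makes the cap per application, and section 4.5.4 applies the hold once an application has already succeeded. The sensible reading is time to abolition followed by consolidation. Saying so would help, but this is a minor clarification.
- **The trial loses power.** The table of assumed losses shows that the documents cannot support a figure, or even a direction.
- **Appendix B changes the endpoint because its footnote omits the condition on appropriate parameters.** Section 2.4 governs, and a form footnote may abbreviate.

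**Conclusion.** Two conflicts stand and should be fixed. First, section 4.5.4 read literally withholds the second EAS application that the primary endpoint allows before mapping is called a failure. Second, the same-target distance is 5 mm in one section and 6 mm in the other, which changes the number of target points for applications 5 to 6 mm apart.

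Confidence is high that the wording conflicts. The effect on results is unknown: it is nil if every centre gives the second EAS application after a failed first, and otherwise depends on shares that the documents do not report. A reader might infer that the sample size is wrong or the trial underpowered on this account. Neither follows: 98 is correct for the stated assumptions, and no loss of power can be quantified.

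**What to change.** 1. In section 4.5.4, state that if the first EAS application fails, a second application with appropriate parameters is given at the EAS before another target point is chosen. The 30-second stop for a failing application can stay.
2. Use one same-target distance in sections 2.4 and 4.5.4, for example the 5 mm of section 2.4, since that is the definitions section.
3. As a minor clarification in section 2.4 and Appendix B, state that the 45-second limit is per application and runs to PVC abolition, and that the 60-second RVOT hold is consolidation. Use the same limit in both places (up to 45 or under 45).

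The cost is wording in three places and a clarified order of applications. The endpoint, the test and the sample size do not change. Recording the time to abolition for each EAS application would be useful but is optional.

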## 2.5 ENDPOINTS

### 2.5.1 PRIMARY ENDPOINT

The primary endpoint will be mapping success using the assigned mapping approach, as defined in the previous section.

### 2.5.2 SECONDARY ENDPOINTS

The following secondary endpoints will be considered:

1. Mapping time.
2. Number of mapped chambers.
3. Accuracy of proposed algorithm (see Appendix C) for selection of first chamber to map.
4. Number of target points.
5. RF time.
6. Number of RF applications.
7. Acute procedure success, as defined in the previous section.
8. Clinical success (reduction of, at least, 80% in the 24-hour PVC burden one month after the procedure).

## 2.6 PATIENT SELECTION CRITERIA

### 2.6.1 INCLUSION CRITERIA

Patients meeting all the inclusion criteria and none of the exclusion criteria could be considered for inclusion in the study. Patients can only be asked to participate if all of the following criteria apply:

- Age > 18 years.
- Indication for PVC ablation.

- Signed informed consent.

#### 2.6.2 EXCLUSION CRITERIA

Patients will be excluded from the study if they meet any of the following criteria:

- Age < 18 years.
- Pregnancy.
- PVC ablation procedures guided by pacemapping (PASO® module); eg. low burden of PVCs during the study, mechanical impact during activation mapping.
- Impossibility to perform activation mapping with the required density of points in the region of interest (see section 4.5.3).
- Concomitant investigation treatments.
- Medical, geographical and social factors that make study participation impractical, and inability to give written informed consent. Patient's refusal to participate in the study.

#### 2.7 STUDY SIZE AND DURATION

100 patients with drug refractory PVCs will be consecutively enrolled and randomized on a 1:1 basis to each of the LAT annotation systems (WF vs. M-method). For more details about sample size calculation, see section 5.1.

An enrollment log with all the patients included in the study, even drops out, will be collected. Data will be collected at enrollment, baseline and at one-month follow-up visit. The total recruitment time will be approximately 12 months (from 5 experienced centers; see next section). The total follow-up time will be one month for each patient. Therefore, the total study duration will be approximately 13 months. Accordingly, the estimated completion date will be approximately by the end of 2018.

## 4. PROTOCOL DESCRIPTION

### 4.1 PROTOCOL PROCEDURES AND OVERVIEW

The following table lists study activities that will be performed at each scheduled visit for all patients enrolled:

PROCEDURES	VISIT	Enrollment	Baseline	Randomization 1:1	Ablation	Pre-discharge	1 Month (+10 days)
Informed Consent		✓					
Inclusion/Exclusion criteria		✓					
Re-evaluation			✓				
Inclusion/exclusion criteria							
Demographic Data			✓				
Medical History			✓				
Pre-procedure MRI (if available)			✓ (*)				
Cardiovascular medication			✓			✓	✓
Transthoracic Echocardiogram (TTE)		✓				✓ (*)	✓
Ablation Data (RF, time, etc.)					✓		
Randomization				✓			
NYHA class			✓				✓
12 lead ECG			✓				✓
24-hour Holter		✓					✓
BNP/NT-proBNP		✓					✓
Protocol Deviation		✓ (*)	✓ (*)	✓ (*)	✓ (*)	✓ (*)	✓ (*)
Adverse Event		✓ (*)	✓ (*)	✓ (*)	✓ (*)	✓ (*)	✓ (*)
Termination		✓ (*)	✓ (*)	✓ (*)	✓ (*)	✓ (*)	✓ (*)

(\*) If applicable

Table 1: List of all investigational specific activities/procedures.

### 4.2 PROTOCOL FLOW

The flow chart of the protocol is the following:

[figure not shown]

Figure 1: Study flow chart.

## 4.3 ENROLLMENT VISIT

### 4.3.1 FIRST TASKS

During the Enrollment visit the following tasks will be completed:

- Patient eligibility check (inclusion/exclusion criteria). Only patients that meet all of the inclusion criteria and none of the exclusion criteria can be approached to participate.
- Patient agrees to participate and signs and dates the patient informed consent.
- Prior reports of cardiac imaging studies (transthoracic echocardiography and/or cardiac magnetic resonance imaging) will be collected, as specified in sections 3.3.2 and 3.3.3.
- Once the patient agrees to participate, a blood test will be given to determine basal levels of BNP or NT-proBNP (according to local hospital policies).
- Once the patient agrees to participate, antiarrhythmic drugs and beta-blockers have to be withdrawn at least for 5 half-lives before the procedure.

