#### 4.4 BASELINE VISIT

The baseline visit must be performed after the patient has signed the informed consent form and prior to the PVC ablation procedure. The patients will be evaluated clinically and the following data will be collected and procedures performed:

- Patient demographic data
- Clinical evaluation with a physical examination
- Medical and cardiovascular history
- Pre-procedure MRI (optional, see before)
- Current cardiac medication (antiarrhythmic drugs and beta-blockers should have been withdrawn at least for 5 half-lives before the procedure)
- NYHA class assessment
- 12-lead ECG
- Adverse Events Notification (if applicable)
- Protocol Deviation (if applicable)
- Termination (if applicable)

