### 4.6 PRE-DISCHARGE

The pre-discharge visit must be performed within 3 days of the ablation procedure and before the patient is discharged from hospital. For all patients, the following procedures must be performed:

- Adverse Events Notification (if applicable)
- Protocol Deviation (if applicable)
- Termination (if applicable)

Regarding medications prior discharge, antiarrhythmic drugs will not be reinitiated after the procedure. A control TTE will be advisable in case any procedure-related complication is suspected. Otherwise, it is not required as per protocol.

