### 4.7 ONE-MONTH FOLLOW-UP

Clinical follow-up will include an outpatient clinic visit one month after ablation procedure. 12-lead ECG and 24-hour ambulatory Holter monitoring will be performed. Successful ablation will be defined as at least an 80% reduction in the 24-hour burden of PVCs at one month post-procedure, since recurrences may be detected very soon after the catheter ablation.

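### The 80% reduction rule for clinical success can compare a baseline Holter taken before drug washout with a one-month Holter taken off antiarrhythmics

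*Combined protocol and SAP*

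**What the plan says.** All references are to the combined protocol and SAP.

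- **Endpoint.** Section 2.5.2, item 8, defines clinical success as a "reduction of, at least, 80% in the 24-hour PVC burden one month after the procedure". Section 4.7 repeats the rule: "Successful ablation will be defined as at least an 80% reduction in the 24-hour burden of PVCs at one month post-procedure". Neither says which earlier recording supplies the denominator.
- **Timing of the recordings.** In Table 1 (section 4.1) the row "24-hour Holter" is ticked at Enrollment and at 1 Month, with no tick at Baseline. The Holter is not among the tasks listed in 4.3.1 or 4.4, so Table 1 is the only place that puts it before ablation.
- **Drugs before the procedure.** Section 4.3.1 says: "Once the patient agrees to participate, antiarrhythmic drugs and beta-blockers have to be withdrawn at least for 5 half-lives before the procedure". Section 4.4 expects the same by the procedure: "antiarrhythmic drugs and beta-blockers should have been withdrawn at least for 5 half-lives before the procedure". Both are tied to the procedure and not to the Holter.
- **Drugs after the procedure.** Section 4.6 says that "antiarrhythmic drugs will not be reinitiated after the procedure". It does not mention beta-blockers. Section 4.7 requires that "12-lead ECG and 24-hour ambulatory Holter monitoring will be performed" and says nothing about drug state.
- **Recording of drugs.** Table 1 schedules cardiovascular medication at Baseline, Pre-discharge and 1 Month, but not at Enrollment.

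**The concern.** A percentage reduction isolates the effect of ablation only if both recordings are made under comparable conditions. Under this schedule, a patient who arrives on an antiarrhythmic or beta-blocker can have the denominator recorded before withdrawal has taken effect. The numerator is recorded a month after ablation, with antiarrhythmics still off. Any suppression by the drug lowers the denominator only, so the recorded reduction understates what ablation achieved.

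Beta-blockers add a second uncertainty. They are withdrawn before the procedure and their status afterwards is not stated. If some patients are back on them at one month and their baseline was off drug, the error runs the other way.

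Clinical success is the only listed endpoint that is measured after the procedure. Because medication at the enrolment Holter is not scheduled to be recorded, a mismatch could not be reliably identified at analysis.

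**Working it through.** **The plan's own figure.** The documents give no rate, power or sample size for clinical success. Their one calculation (section 5.1) concerns mapping success: 60% versus 85%, alpha 5% (two-sided, because the alternative is that the methods are unequal), power 80%. With pooled variance and no continuity correction:

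n per group = [1.960 × √(2 × 0.725 × 0.275) + 0.842 × √(0.60 × 0.40 + 0.85 × 0.15)]² / 0.25² = 48.9, rounded up to 49, or 98 in total.

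This reproduces the stated figure. It does not use the Holter, so the present point leaves it unchanged.

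**Inputs.** The 80% threshold comes from 2.5.2 and 4.7. The fraction s by which drugs suppress PVC burden is not in the documents; s = 10% to 70% is assumed here to show the range. The share of patients on treatment at enrolment is not given either.

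**On-drug baseline, off-drug follow-up.** Let B be the off-drug baseline burden and r the true off-drug reduction.

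- Recorded baseline = (1 − s)B; recorded follow-up = (1 − r)B.
- Recorded reduction = 1 − (1 − r)/(1 − s).
- This reaches 80% only if r ≥ 1 − 0.2(1 − s).

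| Assumed s | True reduction needed | True 80% is recorded as | True 90% is recorded as |
|---|---|---|---|
| 10% | 82% | 77.8% | 88.9% |
| 20% | 84% | 75.0% | 87.5% |
| 30% | 86% | 71.4% | 85.7% |
| 50% | 90% | 60.0% | 80.0% |
| 70% | 94% | 33.3% | 66.7% |

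For example, at s = 20% an off-drug burden of 100 units is recorded as 80. If ablation leaves 20, the recorded reduction is 1 − 20/80 = 75%, a failure, although the true reduction is 80%. With s = 0, or with the same proportional suppression at both recordings, the requirement returns to 80%.

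**Off-drug baseline, suppressed follow-up.** Recorded reduction = 1 − (1 − r)(1 − s), so the rule is met once r ≥ 1 − 0.2/(1 − s). That is 75.0% at s = 20%, 71.4% at 30% and 60.0% at 50%.

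**Who is misclassified.** In the first case, only patients who are on an effective drug at the enrolment Holter and whose true reduction lies between 80% and 1 − 0.2(1 − s).

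**Effect on the difference between arms.** Two invented examples show that its direction is not fixed.

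- True success rates are 75% and 90%, and the same 10% of successes is lost in each arm. The rates become 67.5% and 81%, and the difference shrinks from 15 to 13.5 points.
- All patients are affected at s = 30% (threshold 86%). One arm has 90% of patients above a 95% reduction. The other has 70% above 95% and 15% between 80% and 85%. Everyone else fails under either threshold. The difference grows from 90 − 85 = 5 points to 90 − 70 = 20 points.

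**The case against.** The strongest reply is that no section says the enrolment Holter is taken on drug. Its order relative to withdrawal is not given, and the denominator is not named. This stands: the mismatch is something the plan permits, not something it prescribes. But nothing requires the recording to be off drug, and the visit at which it is scheduled is the one from which withdrawal is first required.

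Exposure may also be small. Being on treatment is not an inclusion criterion (2.6.1), untreated patients are unaffected, and the description of patients as drug refractory in 2.7 suggests limited suppression or drugs already stopped. This stands as a limit on size. It does not remove the problem, because refractory does not mean no suppression, and the data sheet in Appendix B has fields for beta-blockers, amiodarone and flecainide.

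Part of the remedy is already there, since medication is scheduled at Baseline, Pre-discharge and 1 Month. The gap is at Enrollment, where the denominator is recorded.

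A reader might infer more than the documents support:

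- **That success rates are wrong in both arms.** Only treated patients near the threshold are at risk. Patients whose PVCs are almost eliminated, and clear failures, are classified correctly.
- **That the comparison is pulled toward zero.** The drug rules are common to both arms and the enrolment Holter precedes randomization, so nothing points to one arm being favored. But attenuation needs equal sensitivity by arm, which is not shown, and the second example above goes the other way.
- **That objective 3 fails as a whole.** As worded in 2.3, it compares PVC burden at one month, which needs no baseline. Only the 80% definition does.

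**Conclusion.** The point holds for one secondary endpoint. Followed as written, the schedule can put an on-drug baseline and an off-antiarrhythmic follow-up into the same ratio, and the plan has no scheduled record by which to detect this. If drugs suppress baseline burden by 20% to 50%, affected patients need a true reduction of 84% to 90% to be counted as successes. In the reverse situation, at 30% suppression, a true reduction of 71% would be enough.

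These figures rest on an assumed suppression that is the same proportion throughout the recording. How many patients are affected cannot be computed, because neither the share treated nor the suppression is given. Definite misclassification, wrong rates in both arms and a bias toward zero are not established. This is a worthwhile, inexpensive improvement to the plan and no threat to its primary result.

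**What to change.** 1. In Table 1 and section 4.4, time the baseline 24-hour Holter after the washout that 4.3.1 already requires is complete, and before the procedure. Moving the tick from Enrollment to Baseline is not enough: the baseline visit need only fall between consent and the procedure, so it can precede the end of washout. The condition has to be written out.
2. In 2.5.2 (item 8) and 4.7, name that recording as the denominator of the 80% rule.
3. In Table 1 and Appendix B, record antiarrhythmic and beta-blocker status separately at the time of each Holter.
4. In 5.2, add a sensitivity analysis of endpoint 8 limited to patients in the same drug state at both recordings.
5. Reconcile 4.3.1, 4.4 and 4.6 on beta-blockers, which are covered before the procedure and not mentioned after it. No drug rule is proposed here.

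The cost is a few lines of text and one added field per Holter. The test itself is already scheduled. The downside is a later recording that must fit between the end of washout and the procedure, and an existing enrolment Holter may need to be replaced by one taken after washout.
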